4.3.3 LIKELIHOOD OF SMALL VARICES OR VARICES OF ANY SIZE (CLD VALIDATION DATASET)

The analytical and statistical methods described below apply to the **exploratory objectives**. The steps in this analysis are similar to those used in the analysis above for large esophageal varices:

- 1. **Uni-variable Logistic Regression.** Univariate logistic regression analysis will be performed using DSI as the independent variable and varices of any size as the outcome. (see Table **6** for example of the output from this analysis).
- Multi-variable Logistic Regression. As presented above, the gold standard for varices risk by AASLD guidelines is a liver biopsy diagnosis of cirrhosis. In BAVENO VI, platelet count is another major modifier of risk for clinically significant portal hypertension and risk for varices. For these reasons, we will evaluate the independence of DSI as a predictor after taking these variables into account. (see Table 7 for example of the output from this analysis).
- Receiver Operator Curve (ROC) analysis. The diagnostic performance of DSI for predicting varices of any size will be evaluated by Area under the Receiver Operating Curve (AUROC) and c-statistic. The optimum performance characteristics will be defined by Youden Index and sensitivity, specificity, PPV, NPV, NLR, PLR and 95% CIs will be defined over the spectrum of the findings (see Figure 6 for an example of output from this analysis).
- 4. **Probability and Calibration Curves.** The plot of predicted probability of varices of any size versus DSI will be analyzed by linear regression and correlation coefficients and displayed along with 95% confidence intervals (see **Figure 7** and **8** and **Table 8** for example of the output from this analysis).

The diagnostic performance (sensitivity, specificity, PPV, NPV, NLR, PLR) of DSI cutoff 18.3 will be evaluated for esophageal varices of any size. The diagnostic performance of DSI cutoff 18.3 will be compared to the diagnostic performance of a range of DSI cutoffs, as defined from AUROC analysis and Youden Index.

⁵ In this protocol, FNR is defined as 1-NPV and miss rate is defined as 1-Sensitivity. See the footnote in Section 1.1 for a discussion of these two measures.

Although defining likelihood of small varices is not as clinically relevant as defining likelihood of large varices, small varices can progress to large varices and risk for variceal hemorrhage. We would speculate that the small varices with DSI >18.3 are more likely at risk to progress to large varices, than small varices with DSI \leq 18.3. Diagnosing these small varices with EGD generally provides justification for continued EGD surveillance in 1 to 3 year intervals. We speculate that the undetected small varices with DSI \leq 18.3 would likely be the lowest risk varices to either enlarge to large varices or to result in variceal hemorrhage.

4.3.4 STAT EXPLORATORY ANALYSES

The statistical and analytical methods described above for DSI will be applied to the analysis of STAT. The HALT-C Training dataset will be used to define a STAT cutoff for likelihood of large esophageal varices and esophageal varices of any size. The diagnostic performance of the STAT cutoff will then be analyzed in the CLD Validation dataset. Linking STAT to likelihood for large esophageal varices or esophageal varices of any size would provide justification for future development of STAT for this indication.

4.4 Justification for Dose

Dose of 13C-cholate for intravenous injection: 20 mg of 13C-cholate in 5 mL of 8.4% sodium bicarbonate is mixed with 5 mL of 25% human serum albumin prior to injection, and then injected intravenously over 1 minute. The cholate concentration of the initial cholate solution, 4 mg/mL or 10mM, and after mixing with albumin, 2 mg/mL or 5 mM, is below the critical micellar concentration for cholate of 15 mM (104-106).

Albumin binding of cholate further reduces free cholate concentration. Upon mixing, nearly all the cholate binds immediately to albumin which has 7 hydrophobic binding sites for cholate (107). 20 mg cholate equals 50 μ mol cholate; and, 5mL of 25% albumin (Mol Wt. 66,500) contains 1.25 g albumin, or 19 μ mol albumin. Given 7 binding sites for cholate per albumin molecule, 19 μ mol albumin has the capacity to bind 133 μ mol cholate – nearly three times the amount of cholate in the injectate. Pre-binding of the 13C-cholate to albumin reduces free cholate concentrations within the injectate and reduces risk of any adverse detergent effect of cholate on the vein or surrounding tissues.

Dose of d4-cholate for oral administration: 40 mg of d4-cholate in 10 mL of 8.4% sodium bicarbonate is mixed with 10 to 20 mL flavored juice or drink and taken orally. Published studies of intestinal absorption of cholate indicate that absorption approaches 100% when given as a solution (108).

Cholate Blood Concentrations. The blood concentrations achieved after administration of 20 mg of 13C-cholate and 40 mg of d4-cholate in the HepQuant SHUNT test are in the physiologic range. In a mixed population of healthy controls and patients with fibrosis or cirrhosis due to chronic hepatitis C, the peak serum concentrations at 60 minutes after oral administration of 40 mg d4-cholate were $1.2\pm0.5 \mu$ M; peak concentration at 5 minutes after IV administration of 20 mg 13C-cholate were $5.1\pm1.7 \mu$ M (83). These serum concentrations are in the range of the serum concentrations of total bile acids and unconjugated cholate in healthy persons 2 hours after ingestion of a lipid meal: $9.9\pm0.8 \mu$ M and $0.9\pm0.4 \mu$ M, respectively (109). Specific intestinal and hepatic transporters are involved with intestinal absorption and hepatic uptake of cholate (110-112) (see **Appendix B**, Investigator's Brochure).

Maximum Doses:	13C-cholate	Fixed Dose, Intravenous	20 mg
	d4-cholate	Fixed Dose, Oral	40 mg

Study Intervention: None

Control Product: None

4.5 End of Study Definition

A **single participant is considered to have completed the study** if he or she has completed all phases of the study including the last visit or the last scheduled procedure shown in the Schedule of Activities (SoA), **Section 1.4**.

The **end of all patient participation** in the study is defined as the last enrolled patient completing the last visit or procedure shown in the SoA in the trial. The **end of the study** is defined as the completion of all data entry, cleaning of data, analysis of results, presentation of results, and publication of results.

5 STUDY POPULATION

Target Study Population. We plan to enroll up to 420 Adult patients with chronic liver disease from up to 40 clinical centers throughout the United States. The expected composition of our study population is based on a recent publication of USA trends in the burden of healthcare related to chronic liver disease and cirrhosis (56). The expected characteristics of the study population are: gender distribution (M:F) 3:2; mean age 58 years; race/ethnicity with non-Hispanic white 65%, black 12%, Hispanic 17%, and Asian/Pacific Islander 2%; and, etiology of liver disease as viral 15%, Alcohol 34%, and non-alcohol/non-viral 50%.

CLD etiologies. The enrolled CLD patients will be representative of clinical practice in that the cases will span the spectrum of both etiology and severity of liver disease. Etiologies will include chronic hepatitis C (HCV) and B (HBV), alcoholic liver disease, non-alcoholic fatty liver (NAFLD) or steatohepatitis (NASH), primary sclerosing cholangitis (PSC), primary biliary cirrhosis (PBC) and others.

Range of Disease Severity. Severity of disease will encompass noncirrhotic fibrosis stage F3 (with platelet count <175,000 μ L⁻¹), compensated cirrhosis (CP class A), and Child-Pugh class B cirrhosis with exclusion of cases with refractory ascites (continued ascites despite treatment) or refractory encephalopathy (continued encephalopathy despite treatment).

Like HVPG, the HepQuant SHUNT test uniquely targets the portal circulation. For this reason, HepQuant SHUNT could be the minimally invasive alternative to HVPG. This study is critical for defining the performance of DSI in defining likelihood of large varices over an appropriate spectrum of etiology and range of severity of liver disease.

5.1 Inclusion Criteria

The main criteria for enrollment are:

- 1. CLD diagnosis, based upon at least one of the protocol-defined inclusion criteria for CLD (see below),
- 2. CLD etiology, from the list of acceptable protocol-defined etiologies (see below), and
- 3. EGD for the indication of either screening or surveillance for esophageal varices is scheduled or in the process of being scheduled.

The Inclusion Criteria are:

- Signed and dated informed consent
- Stated willingness to comply with all study procedures and availability for the duration of the study
- Adult male or female, age at entry at least 18 years
- Adequate peripheral venous access for intravenous catheter
- Ability to take the oral dose of d4-cholate
- Ability to hold morning doses of medications (Non-Selective Beta Blocker, ARB and/or Ace Inhibitor) for the 90 minute duration of the HepQuant SHUNT Test
- Meets at least one of the following criteria for CLD:
 - Abnormal liver enzymes (AST, ALT, or alkaline phosphatase), or, abnormal direct bilirubin, albumin, or INR (liver-related) of greater than 6 months duration. These subjects must also have platelet count <175,000 μL⁻¹
 - \circ Fibrosis stage 3 (F3) or higher by liver biopsy (by METAVIR, Batts-Ludwig, or Brunt-Kleiner). Patients with F3 fibrosis must have platelet count <175,000 μ L⁻¹
 - \circ Fibrosis stage 3 or higher by elastography (FibroScan, SuperSonic, or MRE). Patients with F3 fibrosis must have platelet count <175,000 μ L⁻¹
 - $\circ~$ Fibrosis stage 3 or higher by FDA-approved laboratory panels. Patients with F3 fibrosis must have platelet count <175,000 $\mu L^{\text{-1}}$
 - Child-Pugh class A or B cirrhosis

- HVPG of 6 mmHg or higher
- Radiologic imaging consistent with either cirrhosis or portal hypertension
- Has one of the following diagnoses of CLD:
 - Hepatitis C virus (HCV) infection with documentation of a prior positive HCV RNA. Patients who achieved virologic cure are eligible to participate as long as they have CLD as defined above
 - Hepatitis B virus (HBV) infection defined by positive HBsAg
 - Non-alcoholic steatohepatitis (NASH)
 - Cryptogenic cirrhosis
 - Alcoholic liver disease
 - o Cholestatic liver disease
 - Primary biliary cholangitis (PBC)
 - Primary sclerosing cholangitis (PSC)
 - Autoimmune hepatitis
 - Inherited disorders causing CLD
 - Hereditary hemochromatosis
 - Alpha-1-antitrypsin deficiency
 - Wilson disease
- Scheduled, or in the process of being scheduled for EGD

Indications for EGD. A key inclusion criteria is that the subject must have been selected and scheduled or in the process of being scheduled for EGD for the indication of either screening or surveillance for esophageal varices. Patients who are known to have had large esophageal varices on prior endoscopy or who have undergone treatment for varices, either radiologically (TIPS), surgically (Portal-Systemic Shunt), or endoscopically (banding or sclerotherapy) are excluded. Patients with prior endoscopic diagnosis of small esophageal varices who are undergoing EGD for surveillance of varices may be included.

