2.1.2 STUDY POPULATION AND DISEASE

The **CLD Validation dataset** will consist of subjects with CLD who have been selected for EGD to screen or undergo surveillance for esophageal varices.

Definition of CLD. CLD is defined as a disease process of 6 months or more in duration, characterized by ongoing liver injury and progression of fibrosis, culminating in its most severe form as cirrhosis with clinical complications (12). The SHUNT-V study is focused on CLD cases with F3 or F4 (cirrhosis) stages of disease. Etiologies of CLD include chronic viral hepatitis (hepatitis B and C), alcoholic liver disease, non-alcoholic fatty liver disease (NAFLD) or steatohepatitis (NASH), cholestatic liver disease (primary biliary cholangitis, primary sclerosing cholangitis), and genetic disorders such as hemochromatosis, Wilson's disease, and alpha-1-antitrypsin deficiency.

Prevalence of CLD. CLD is highly prevalent and global in reach. Up to 30% of the general adult population has steatosis and 6 to 7% has liver fibrosis, mostly associated with NAFLD, prompting suggestions for population screening (13-15). A European study of LSM measurement in over 3000 healthy asymptomatic persons without known liver disease found that 3.6% have "silent" significant fibrosis (fibrosis stages F2 to F4 (cirrhosis)) defined by transient elastography of kPa >9.0. Liver biopsy was performed in 92 cases and 16% had F3 or F4 fibrosis (16).

CLD Stage and Risk for Varices. Patients with F3 fibrosis have a pre-cirrhotic stage of fibrosis but are at risk for portal hypertension and varices. Results from the whole HALT-C study demonstrated that 2% of subjects with bridging fibrosis (13/598) and 11% of those with cirrhosis (48/418) had large varices. Twenty one percent (13/61) of the large varices occurred in subjects with bridging fibrosis (17). Platelet count >150,000 μ L⁻¹ excluded nearly all the cases with large varices.

In the **HALT-C Training dataset**, 4% of subjects with bridging fibrosis (5/124) and 18% of those with cirrhosis (17/93) had large varices. 23% percent of the large varices occurred in subjects with bridging fibrosis. Platelet count >175,000 μ L⁻¹ excluded all the cases with large varices.

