Both F3 and F4 cases are included in the SHUNT-V study, but a requirement for subjects with non-cirrhotic F3 disease is a platelet count <175,000 μ L⁻¹. SHUNT-V does not have a platelet count requirement for F4 cases, since diagnosis of cirrhosis is a risk factor for large varices independent of platelet count.

Esophageal Varices. All CLD, regardless of etiology, progresses via inflammation and fibrosis to alter portal blood flow, which may ultimately lead to portal hypertension and portal-systemic shunts (18). Esophageal varices are portal-systemic shunts and the HepQuant SHUNT Test quantifies portal-systemic shunting.

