4.3 Validating DSI Cutoff 18.3 in the CLD Validation Dataset

4.3.1 DESCRIPTION OF THE CLD VALIDATION DATASET

Characteristics of CLD Patients: The goal is to recruit a population of patients with chronic liver disease (CLD) that spans the spectrum of severity and etiologies of CLD to encompass all CLD patients meeting criteria for EGD to screen for varices. The inclusion and exclusion criteria were selected to encompass severity of CLD ranging from non-cirrhotic fibrosis with low platelet count to moderately compensated Child-Pugh B cirrhosis and to achieve an overall prevalence of large esophageal varices of $\geq 20\%$. Enrolled subjects must satisfy 4 main criteria:

- Meets the protocol-defined definition for chronic liver disease (CLD).
- For patients with CLD with non-cirrhotic F3 disease, platelet count must be <175,000 μL⁻¹. The BAVENO VI criteria used platelet count cutoff of 150,000 μL⁻¹ to enhance the diagnostic performance of LSM. Others have used lower platelet counts of 100,000, 110,000, and 120,000 μL⁻¹. The lower the platelet count the higher the likelihood of large varices or varices of any size. But, as the cutoff for platelet count decreases the number of missed cases of large varices increases.

The goal of the DSI cutoff \leq 18.3 is exclusion of all cases with large esophageal varices. In the HALT-C Training dataset, the prevalence of large varices was 18.3% (17/93) in the cases with F4 fibrosis (cirrhosis), and similar, at 21.8% (17/78), in F4 cases with platelet count <175,000 μ L⁻¹. I n contrast, the prevalence of large varices was 9% (4/44) in all cases with F3 fibrosis, but much higher, at 16% (4/25), in the F3 cases with platelet count <175,000 μ L⁻¹. There was no case of large varices in the cases with \leq F3 fibrosis and platelet count <175,000 μ L⁻¹.

Applying this platelet count requirement to cirrhotic cases would not enhance the prevalence of large varices in cirrhotic cases but would increase prevalence of large varices in F3 fibrosis. In addition, AASLD and EASL guidelines state that cirrhosis, independent of platelet count, is a risk factor for large esophageal varices. For these reasons, our study only requires a platelet count <175,000 μ L⁻¹ for non-cirrhotic F3 cases. There is no platelet count requirement for enrollment of cases with cirrhosis.

- Meets one of the protocol-defined etiologies for CLD.
- Is scheduled or in the process of being scheduled for EGD.

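### Section 5.1 admits subjects outside the stated population of cirrhosis or low-platelet F3, and no planned analysis would show their effect on the NLR result

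*Combined protocol and SAP*

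**What the plan says.** Section 5.1 sets the rule "Meets at least one of the following criteria for CLD" and lists seven items.

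- **Enzyme/function item:** "Abnormal liver enzymes (AST, ALT, or alkaline phosphatase), or, abnormal direct bilirubin, albumin, or INR (liver-related) of greater than 6 months duration". The added condition is "These subjects must also have platelet count" below 175,000. No fibrosis stage or cirrhosis finding is required.
- **Biopsy, elastography and laboratory-panel items:** stage 3 or higher, each with the rider "Patients with F3 fibrosis must have platelet count" below 175,000.
- **Child-Pugh A or B cirrhosis.**
- **HVPG of at least 6 mmHg**, and **imaging suggesting cirrhosis or portal hypertension**. Neither carries a stage or platelet condition.

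Sections 1.4 and 8.1 add that biopsy, elastography, blood panels and HVPG are not needed for enrollment.

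Other sections describe a narrower population. Section 2.1.2 says "The SHUNT-V study is focused on CLD cases with F3 or F4 (cirrhosis) stages of disease" and that "a requirement for subjects with non-cirrhotic F3 disease is a platelet count <175,000". Section 4.3.1 makes the same platelet limit one of four main criteria, whatever the route of entry. Section 5 says "Severity of disease will encompass noncirrhotic fibrosis stage F3" with the platelet limit, plus Child-Pugh A and B cirrhosis. Sections 4.3.1 and 9.6 define three severity categories on the same lines. Sections 1.1 and 1.2 are wider: they add suspected cirrhosis shown by surrogate tests.

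**The concern.** Read literally, 5.1 opens two routes that the population statements close. A subject with biopsy stage F1-F2, raised ALT for more than six months and platelets of 170,000 qualifies on the enzyme item. A non-cirrhotic F3 subject with platelets of 220,000 fails the biopsy item but can qualify on HVPG or on imaging of portal hypertension. The first fits none of the three severity categories. The second fits only if the platelet condition is ignored.

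Two opposite effects are at stake. Section 5.2 says DSI rises with fibrosis stage, so lower-stage subjects may be mostly test-negative without large varices. They would then raise specificity and lower the pooled NLR without better rule-out in the intended population. They would also bring few large-varices cases, and Section 4.1.1 rests the 20% prevalence on the inclusion criteria.

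No planned analysis separates these subjects. Section 9.3 lists no sensitivity datasets and defines per-protocol as completing the protocol. The primary-endpoint subgroups in Section 9.6.1.1 are age, sex, race and etiology.

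**Working it through.** **1. The plan's own figure.** Section 9.2.1 assumes NLR 0.20, sensitivity 0.90, specificity 0.50, N = 400 and V = 80 cases. Equation E of Table 9 gives

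Var(ln NLR) = 0.90/(0.10 × 80) + 0.50/(0.50 × 320) = 0.1125 + 0.0031 = 0.1156, so SE = 0.340.

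- Power = Φ[ln(0.52/0.20)/0.340 − 1.96] = 0.802 (stated 0.80).
- Critical value = 0.52 × exp(−1.96 × 0.340) = 0.267 (stated 0.27).

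Both reproduce.

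**2. Prevalence in the extra subjects.** In the HALT-C training set, Section 2.1.2 gives 5/124 large varices in bridging fibrosis, and Section 4.3.1 says "the prevalence of large varices was 9% (4/44) in all cases with F3 fibrosis" and 4/25 in low-platelet F3.

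- Non-cirrhotic other than F3: 124 − 44 = 80 subjects, 5 − 4 = 1 case (1.25%). This assumes that the two sections use one staging scale.
- F3 without low platelets: 44 − 25 = 19 subjects, 4 − 4 = 0 cases.

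**3. Loss of cases and power.** Let a share f of 400 enter by these routes at 1.25% prevalence, with 20% in the rest. The value of f is assumed.

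- f = 10%: (360 × 0.20 + 40 × 0.0125)/400 = 18.1%, 72.5 cases, power 0.764, critical value 0.258.
- f = 20%: (320 × 0.20 + 80 × 0.0125)/400 = 16.25%, 65 cases, power 0.719, critical value 0.249.

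At 0% prevalence the powers are 0.761 and 0.713. All hold true NLR at 0.20.

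**4. Effect on the decision.** Section 9.5.1 sets a 96.07% confidence level at N = 400, and Section 9.4.2 specifies a score interval. The upper limit is the θ that solves

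(p₁ − θp₂) / √[p̃₁(1 − p̃₁)/V + θ²p̃₂(1 − p̃₂)/(N − V)] = −2.06,

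where p₁ = 1 − sensitivity, p₂ = specificity, and the tildes mark estimates constrained to p̃₁ = θp̃₂. I used expected counts and held sensitivity at 0.86 overall. The assumed specificity in the extra subjects is 0.75-0.90.

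Example of pooling, with intended-population specificity 0.46: f = 10% and 0.75 give (288 × 0.46 + 39.5 × 0.75)/327.5 = 0.495; f = 20% and 0.90 give (256 × 0.46 + 79 × 0.90)/335 = 0.564.

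| Specificity, intended population | NLR, intended only | Upper limit, intended only | Upper limit, f = 10%, specificity 0.75 | Upper limit, f = 20%, specificity 0.90 |
|---|---|---|---|---|
| 0.44 | 0.318 | 0.551 (fail) | 0.518 (pass) | 0.462 (pass) |
| 0.46 | 0.304 | 0.526 (fail) | 0.499 (pass) | 0.449 (pass) |
| 0.50 | 0.280 | 0.483 (pass) | 0.465 (pass) | 0.426 (pass) |

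With 5% prevalence in the extra subjects instead of 1.25%, the pooled limits are 0.517 to 0.459 in the first row and 0.498 to 0.447 in the second. The conclusion does not depend on the 1.25%.

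**The case against.** The other side has five arguments.

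- **Suspected cirrhosis.** Sections 1.1 and 1.2 include it, and Section 1.2 allows a biochemical diagnosis of cirrhosis. Chronic abnormal tests, low platelets and selection for variceal EGD fit much of that description. This stands in part: some enzyme-item subjects belong. But 5.1 requires neither suspicion nor a surrogate test for cirrhosis, and Sections 2.1.2 and 5 have no such limb.
- **The F3 platelet rule is already general.** Section 4.3.1 binds every enrolled subject, so the intent is clear. That stands. The operative list still does not carry the rule to the HVPG and imaging items. Imaging of cirrhosis is not at issue, since Section 1.2 accepts it as a diagnosis; the gap is the portal-hypertension part.
- **Exclusions and EGD selection limit the numbers.** The Section 5.2 exclusion of noncirrhotic causes of portal hypertension may narrow the imaging route, and clinicians choose who has EGD. Neither sets a fibrosis stage or a platelet limit.
- **The reference prevalence is imperfect.** The 80 subjects were not selected for low platelets, and Section 2.1.2 says platelets above 175,000 excluded every large-varices case. Prevalence in enzyme-item subjects may therefore exceed 1.25%. The 0/19 were not selected for portal hypertension. Both limits stand.
- **No decision need change.** A reader might infer that pooling carries a failing test across the plan's 0.27 threshold, for example from 0.28 to 0.26-0.24 at sensitivity 0.86. The documents do not support that. The 0.27 is an approximation at design values and falls to about 0.26-0.25 as cases are lost. On the planned score interval the 0.28 result already passes (0.483).

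**Conclusion.** The contradiction in the text is real: 5.1 admits subjects whom Sections 2.1.2, 4.3.1 and 5 exclude, and no planned analysis would reveal their influence. Its size is unknown because the share of such subjects is not in the documents.

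Under the assumptions in the working, a test that fails the NLR goal in the intended population could pass in the enrolled one when intended-population specificity is about 0.44-0.46. At the design value of 0.50 the decision is unchanged. If the extra subjects do not lower the NLR, the effect runs the other way, with power of about 0.76 at a 10% share and 0.71-0.72 at 20%.

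A reader might infer that the criteria bias the trial toward success, or that the extra subjects are all easy true negatives. The documents establish neither. The specificity of 0.75-0.90 is assumed, and those entering on HVPG or imaging do so because portal hypertension is suspected. The supported conclusion is that eligibility and stated population disagree, and that the effect should be measured.

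**What to change.** 1. **Reconcile the text.** The sponsor should bring Section 5.1 into agreement with Sections 2.1.2, 4.3.1 and 5, and with the suspected-cirrhosis wording in Sections 1.1 and 1.2, so that the enrolled population, the F3 platelet rule and the severity categories match. Which eligibility rule is right is for the sponsor to decide.
2. **Pre-specify one sensitivity analysis** of NLR, sensitivity and specificity at DSI 18.3. Exclude subjects whose only qualifying item is the enzyme/bilirubin/albumin/INR one, and non-cirrhotic F3 subjects with platelets of 175,000 or more. Report the number of subjects in each excluded group. The primary analysis stays as planned.

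Sections 1.5 and 8.2 show that CLD criteria and blood counts are already collected. The sponsor should confirm that the case report form records every item met, since the exclusion depends on the only item met. The cost is one extra analysis with a somewhat wider interval. It may also drop some subjects who truly had suspected cirrhosis, so it should be read beside the primary result.
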